**5) Prohibited Treatments and/or Therapies**

- a. Subjects who have at any time received treatment with any investigational drug within 28 days (or less than 5 terminal half-lives of elimination) of the Day 1 dose.
- b. Any concomitant biologic DMARD, such as anakinra.
- c. Subjects who have been treated with intralesional steroids, systemic steroids, anthralin, squaric acid, DPCP (diphenylcycloprophenone), topical, minoxidil or other medication which in the opinion of the investigator may affect hair regrowth within one month of the baseline visit.

**6) Other Exclusion Criteria**

- a. Prisoners or subjects who are involuntarily incarcerated.
- b. Subjects who are compulsorily detained for treatment of either a psychiatric or physical (e.g, infectious disease) illness.

Eligibility criteria for this study have been carefully considered to ensure the safety of the study subjects and to ensure that the results of the study can be used. It is imperative that subjects fully meet all eligibility criteria.

**4.2.3 Women of Childbearing Potential**

Women of childbearing potential (WOCBP) include any female who has experienced menarche and who has not undergone successful surgical sterilization (hysterectomy, bilateral tubal ligation, or bilateral oophorectomy), and who is not postmenopausal. Post menopause is defined as:

- Amenorrhea ≥ 12 consecutive months without another cause, and a documented serum follicle stimulating hormone (FSH) level > 35 mIU/mL or
- Women with irregular menstrual periods and a documented serum follicle stimulating hormone (FSH) level > 35 mIU/mL or
- NOTE: FSH level testing is not required for women ≥ 62 years old with amenorrhea of ≥ 1 year
- Women on hormone replacement therapy (HRT)

Women who are using oral or other hormonal contraceptives, such as vaginal products, skin patches, or implanted or injectable products, or mechanical products, such as an intrauterine device or barrier methods (diaphragm, condoms, spermicides), to prevent pregnancy or who are practicing abstinence or who have a sterile (e.g., vasectomy) partner should be considered to be of childbearing potential.

Not Applicable.

### **4.3 Concomitant Treatments**

#### **4.3.1 Prohibited and/or Restricted Treatments**

Any medication known to affect hair growth in Alopecia areata including but not limited to topical, intralesional or systemic steroids, squaric acid, anthralin, protopic, minoxidil, diphenylcyclopropenone, cyclosporine and any other medications, which in the judgment of the investigator, may affect hair growth in patients with alopecia areata.

#### **4.3.2 Other Restrictions and Precautions**

Not applicable.

### **4.4 Discontinuation of Subjects from Treatment**

Subjects MUST discontinue study treatment and withdraw from the study for any of the following reasons:

Withdrawal of informed consent (subject's decision to withdraw for any reason)

Any clinical adverse event (AE), laboratory abnormality, or intercurrent illness which, in the opinion of the investigator, indicates that continued participation in the study is not in the best interest of the subject

Pregnancy

- Instruct WOCBP to contact the investigator or study staff immediately if they suspect they might be pregnant (eg, missed or late menstrual period) at any time during study participation. Institutional policy and local regulations should determine the frequency of on-study pregnancy tests for WOCBP enrolled in the study.
- The investigator must immediately notify BMS if a study subject becomes pregnant. The mechanism for reporting pregnancy is described in Section 7.6.

Termination of the study by BMS.

Loss of ability to freely provide consent through imprisonment or involuntarily incarceration for treatment of either a psychiatric or physical (eg, infectious disease) illness.

## **5 TREATMENTS**

### **5.1 Study Treatment: Abatacept**

An investigational product, also known as investigational medicinal product in some regions, is defined as follows: A pharmaceutical form of an active substance being tested or used as a reference in a clinical study, including products already with a marketing authorization but used or assembled (formulated or packaged) in a way different from the authorized form, or used for an unauthorized indication, or when used to gain further information about the authorized form. In this protocol, the investigational product is abatacept.

Other medications used in the study as support or escape medication for preventative, diagnostic, or therapeutic reasons as components of a given standard of care are considered noninvestigational products.

#### **5.1.1 Identification**

Abatacept Injection, 125 mg/Syringe (125 mg/mL), is a sterile solution for SC administration, which contains approximately 126 mg abatacept, 171 mg sucrose, 8 mg Poloxamer 188, 0.28 mg monobasic sodium phosphate, monohydrate, and 0.84 mg dibasic sodium phosphate, anhydrous, in Water for Injection. It is packaged in 1 mL long glass syringe barrel staked with a 29 gauge stainless steel needle and stoppered with a 7.1 mm rubber stopper. The composition of this solution has a ratio of monobasic sodium phosphate, monohydrate, and dibasic sodium phosphate, anhydrous, used to achieve the target pH of 7.2.

#### **5.1.2 Storage, Handling, and Dispensing**

The investigational product should be stored in a secure area according to local regulations. The investigator is responsible for ensuring that it is dispensed only to study subjects and only from official study sites by authorized personnel, as dictated by local regulations.

All investigational product supplies that will be used in the study must be maintained securely under the direct responsibility of the investigator or delegated by the investigator to the hospital pharmacist, or other personnel licensed to store and dispense drugs. All drugs shall be dispensed in accordance with the investigator's responsibility to ensure that an accurate record of drugs issued and returned is maintained.

The investigator is responsible for ensuring that the investigational product is stored under the appropriate environmental conditions (temperature, light, and humidity), as determined by the sponsor and defined by the Investigator Brochure or SmPC/ reference label. If concerns regarding the quality or appearance of the investigational product arise, do not dispense the investigational product and contact the sponsor immediately. Care should be taken when handling the injectable drug products that are used in this protocol. Proper aseptic techniques must be used when preparing and administering sterile parenteral products such as abatacept. Parenteral drug products should

be inspected visually for particulate matter prior to administration. Refer to the Investigator Brochure for additional information regarding handling, preparation, and storage of abatacept.

### **5.1.3 Additional Information for the Handling, Dispensing, and Storage of Abatacept**

Abatacept injection, 125 mg/syringe (125 mg/mL) for SC administration are ready to use solutions provided in pre-filled siliconized syringes with a 29 gauge needle. No special drug preparation is required prior to administering to patients. A sufficient amount of abatacept solution is incorporated into each syringe so that 1 ml of solution will be administered upon administration.

Abatacept SC formulations (prefilled syringes) should be stored under refrigeration (approximately 2 to 8°C) and protected from long-term (more than 24 hours) exposure to light. Do not freeze.

Additional information on the use of the abatacept combination product is found in the Appendix.

## **5.2 Method of Assigning Subjects to a Treatment**

This will be an open label study. All subjects will receive active drug for the duration of the 6 month treatment period.

## **5.3 Selection and Timing of Dose for Each Subject**

Patients will be treated with abatacept 125mg SC self-administered each week. Treatment will be continued for 6 months to provide adequate time to assess the short-term efficacy and safety of abatacept in patients with alopecia areata. Patients will then be followed for an additional 6 months to assess the timing and incidence of relapse.

### **5.3.1 Dose Modifications for Adverse Events**

If there is evidence of toxicity, as determined by laboratory tests or by clinical assessment that could place the subject at increased risk in the judgment of the investigator, administration of abatacept should be interrupted and the investigator should notify BMS. Subjects may be considered eligible to continue with abatacept treatment only if full resolution of the adverse event is documented. If the adverse event completely resolves and the next dose of abatacept cannot be administered within 14 days of the target date, then that scheduled dose should be skipped. The next dose of abatacept should then be administered on the next targeted day for administration.

## **5.4 Blinding/Unblinding**

Not applicable.

## **5.5 Concomitant Treatments**

### **5.5.1 Prohibited and/or Restricted Treatments**

The following medications are prohibited throughout the complete study period:

Any medications known to affect hair growth in alopecia areata including but not limited to topical, intralesional or systemic steroids, anthralin, squaric acid, diphenylcyclopropenone, topical, cyclosporine or any other medications which in the opinion of the investigator may affect hair growth in AA.

Live vaccines.

Use of any investigational drug other than study medication.

Corticosteroid use at unstable dose and/or superior to the equivalent of prednisone 10 mg/day is not permitted.

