### *Current therapeutic options for Alopecia Areata*

**There is no FDA approved drug for alopecia areata.** A recent Cochrane report (Delamere et al, 2008) concluded that there was no evidenced based support for any intervention in this disease. Standard of care remains observation for mild disease, and lesional/oral steroids for more advanced cases (Alkhalifah et al, 2010a,b). **In our targeted population of moderate-severe alopecia areata placebo response rates have been in the 6-12% range** (Price et al, 2008; Strober et al, 2009). Spontaneous regrowth is extremely rare in patients with alopecia totalis or universalis. Intralesional steroid responses are unpredictable and occur less frequently in subjects with higher disease burdens. This population that suffers from a disfiguring disease represents a significant unmet medical need (Alkhalifah et al, 2010a,b). Evidence-based and steroid-sparing interventions are needed.

Use of subcutaneous Abatacept carries potential risks, including treatment-associated infection and injection site reactions. **Alopecia areata patients as a whole are young (median age 23-30) and otherwise healthy, which should mitigate risk of adverse effects.** The target population in this proposed study is subjects with greater than 30% hair loss is unusually extensive disease, affecting fewer than 30% of all alopecia subjects, with disfiguring consequences and severe psychosocial morbidity. Although AA does not cause physical pain, several studies have noted that AA seriously impairs quality of life (QoL), mainly by altering self-perception and self-esteem, both of which interfere with social life. **Because AA is chronic, visible to others, and often difficult to treat, its impact on quality of life is underappreciated (Bickers et al, 2006; Hanan et al, 2008; Dubois et al, 2010)** and comparable to psoriasis (Bickers et al, 2006). Patient advocacy groups, including National Alopecia Areata Foundation have developed an active disease registry of over 10,000 subjects to document the impact on quality of life and encourage clinical investigation in this disease.

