## 2) **Target Disease Exceptions**

- a. Two to five patients with current alopecia totalis/universalis at the time of enrollment (i.e. 100% scalp or 100% scalp and body loss, respectively) may be enrolled. The remaining patients must have 30 to 95% hair loss due to alopecia areata.
- b. Patients with a history of or active skin disease on the scalp such as psoriasis or seborrheic dermatitis.
- c. Patients in whom the diagnosis of alopecia areata is in question.
- d. Patients with active medical conditions or malignancies (except adequately treated basal or squamous cell carcinoma) that in the opinion of the investigator would increase the risks associated with study participation, including patients with a history of recurrent infections.
- e. Patients with COPD
- f. Patients known to be HIV or hepatitis B or C positive.
- g. Patients with history or evidence of hematopoietic abnormality.
- h. Patients with history of immunosuppression or history of recurrent serious infections.
- i. Patients unwilling or unable to discontinue treatments known to affect hair regrowth in AA

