## 3) **Coexisting disease or concurrent medications**

- a. Patients taking TNF antagonists or other biological therapy such as anakinra.
- b. Patients known to be HIV or hepatitis B or C positive.
- c. Patients with evidence of infection or active/untreated skin cancer.
- d. Patients who have been treated with intralesional steroids, systemic steroids, anthralin, squaric acid, DPCP (diphenylcycloprophenone), topical, minoxidil or other medication which in the opinion of the investigator may affect hair regrowth within one month of the baseline visit.

- e. Subjects who are impaired, incapacitated, or incapable of completing study-related assessments.
- f. Subjects with current symptoms of severe, progressive, or uncontrolled renal, hepatic, hematologic, gastrointestinal, pulmonary, cardiac, neurologic, or cerebral disease, which, in the opinion of the investigator, might place a subject at unacceptable risk for participation in the study.
- g. Female subjects who have had a breast cancer screening that is suspicious for malignancy and in whom the possibility of malignancy cannot be reasonably excluded by additional clinical, laboratory, or other diagnostic evaluations.
- h. Subjects with a history of cancer in the last 5 years, other than non-melanoma skin cancers cured by local resection or carcinoma in situ. Existing non-melanoma skin cancers should be removed, the lesion site healed, and residual cancer ruled out before administration of the study drug.
- i. Subjects who currently abuse drugs or alcohol.
- j. Subjects with evidence (as assessed by the investigator) of active or latent bacterial or viral infections at the time of potential enrollment, including subjects with evidence of human immunodeficiency virus (HIV) detected during screening.
- k. Subjects with herpes zoster or cytomegalovirus (CMV) that resolved less than 2 months before the informed consent document was signed.
- l. Subjects who have received any live vaccines within 3 months of the anticipated first dose of study medication.
- m. Subjects with any serious bacterial infection within the last 3 months, unless treated and resolved with antibiotics, or any chronic bacterial infection (eg, chronic pyelonephritis, osteomyelitis, or bronchiectasis).

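### Section 5.5.1 bans systemic steroids at any dose and then bars them only above a threshold, and no rule says how a subject who starts steroids on study counts in the week-24 response rate

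*Combined protocol and SAP*

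**What the plan says.** Section 5.5.1 opens with "The following medications are prohibited throughout the complete study period". Its first item covers medications known to affect hair growth in alopecia areata, "including but not limited to topical, intralesional or systemic steroids, anthralin, squaric acid" and others. Systemic steroids are named without a dose limit. The last item of the same list reads "Corticosteroid use at unstable dose and/or superior to the equivalent of prednisone 10 mg/day is not permitted".

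Four other places bear on the same drugs, and none has a threshold:

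- Section 4.3.1 restricts medications affecting hair growth, "including but not limited to topical, intralesional or systemic steroids, squaric acid, anthralin, protopic, minoxidil" and others.
- Exclusion 3d in Section 4.2.2 ("Patients who have been treated with intralesional steroids, systemic steroids, anthralin, squaric acid, DPCP" and others) applies to treatment within one month of baseline.
- Exclusion 5c ("Subjects who have been treated with intralesional steroids, systemic steroids, anthralin, squaric acid, DPCP" and others) repeats it.
- Exclusion 2i removes "Patients unwilling or unable to discontinue treatments known to affect hair regrowth in AA".

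The primary endpoint (Section 6.4.1) is the proportion of subjects whose SALT score has improved by at least half at week 24. It sets no condition on concomitant medication. Section 7.4.3 plans descriptive summaries and does not say how a subject who took a prohibited medication is classified. Section 4.4 does not name such use among the reasons for discontinuation.

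**The concern.** Two sentences in one list give different answers to one question: may a subject take a low, stable dose of a systemic corticosteroid during the study? Site staff could follow either sentence and believe that they were complying.

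The answer bears on the primary endpoint. The protocol itself classes systemic steroids among medications that affect hair growth in this disease. In Section 1.4, under current therapeutic options, it gives the standard of care as "lesional/oral steroids for more advanced cases". The trial is single-arm and open-label, so no concurrent group would show the same steroid effect. If a subject who started a steroid after baseline regrew enough hair, that subject would count as a responder under the endpoint as written. Without a rule set in advance, the classification would be decided by people who already know the outcome.

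**Working it through.** **Step 1. The passages side by side**

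| Place | Period covered | Systemic steroid rule |
|---|---|---|
| 5.5.1, first item | Complete study | Prohibited, no dose limit |
| 5.5.1, last item | Complete study | Barred if dose unstable and/or above prednisone 10 mg/day equivalent |
| 4.3.1 | On study (concomitant treatments) | Restricted/prohibited, no dose limit |
| Exclusions 3d, 5c | One month before baseline | Excluded, no dose limit |
| Exclusion 2i | Entry | Excluded if unable or unwilling to stop |

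If the first row governs, the second adds nothing. If the second has a function, the first is not absolute. The last item is expressed in prednisone equivalents, so it concerns systemic exposure. No passage limits it to another indication or ranks the two items.

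**Step 2. Who could be affected**

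A subject already on a systemic steroid in the month before baseline is excluded at any dose. What remains is mainly a subject who starts one after baseline and before the week-24 SALT. Only 4.3.1 and 5.5.1 govern that period, and the conflict lies in 5.5.1.

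**Step 3. The plan's own figure**

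Section 7.1 gives N = 15, a historical rate of 10%, a difference of 30 points (so 40%), alpha 5% with sidedness not stated, and power 80.7%.

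- Arcsine approximation, two-sided: Φ[(2·asin√0.40 − 2·asin√0.10)·√15 − 1.96] = 80.3%.
- Normal approximation with continuity correction, two-sided: Φ{[(0.30 − 1/30)·√15 − 1.96·√(0.10·0.90)] / √(0.40·0.60)} = 81.8%.

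Both lie within about one point of 80.7%. Reconciling the steroid text changes neither N nor this calculation.

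**Step 4. Size of one affected responder (illustration)**

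Assumption: exactly one counted responder owes the response to a steroid. The response rate moves by 1/15 = 6.7 points. With X ~ Binomial(15, 0.10), the probabilities of 0, 1, 2, 3 and 4 responders are 0.2059, 0.3432, 0.2669, 0.1285 and 0.0428.

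- P(X ≥ 4) = 1 − (0.2059 + 0.3432 + 0.2669 + 0.1285) = 0.056.
- P(X ≥ 5) = P(X ≥ 4) − 0.0428 = 0.013.

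**Step 5. A range, because the documents give no inputs**

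Assume that abatacept is inactive, that k subjects start steroids and respond with probability s, and that the other 15 − k respond at 10%. The responder count is then Binomial(15 − k, 0.10) + Binomial(k, s). Both k and s are assumptions.

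| k | s | P(≥ 4 of 15) | P(≥ 5 of 15) |
|---|---|---|---|
| 0 | – | 5.6% | 1.3% |
| 1 | 0.20 | 6.7% | 1.6% |
| 1 | 0.50 | 10.1% | 2.7% |
| 2 | 0.20 | 8.0% | 2.0% |
| 2 | 0.50 | 17.0% | 5.2% |
| 3 | 0.20 | 9.4% | 2.5% |
| 3 | 0.50 | 26.2% | 9.4% |

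**The case against.** The strongest reply is that no sentence grants permission. The last item of 5.5.1 is itself a prohibition, in a list of prohibitions, and the unqualified ban appears there and again in 4.3.1. Subjects on a stable dose at entry are excluded, and a newly started course may not be a stable dose at all. On this view the clause is redundant. That stands as an argument about likelihood: few subjects could come under the clause. It does not settle which item governs once a subject does.

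A reader might also infer from the differing lists that some drugs escape one section. Section 4.3.1 names protopic and minoxidil, and 5.5.1 names neither. The documents do not support that inference: both lists are expressly non-exhaustive, and both end with a catch-all for anything the investigator judges may affect hair growth.

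A third objection is that use would not go unseen. The visit lists and Table 3 provide for concomitant medication review at every study visit from baseline, and with 15 subjects at one site a steroid user would be visible. That is correct, and it means the data for a rule already exist. It does not supply the rule.

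Finally, the p-values in Step 4 are not specific to steroids. A single misclassification from any cause has the same effect, and the step from 5 to 4 is the only one that crosses one-sided 5%. This stands, and the figures should be read only as a scale.

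**Conclusion.** Wrong as written. Section 5.5.1 contradicts itself on systemic corticosteroids, and the analysis section does not say how on-study use affects the responder count. The correction should be made, but the practical exposure is small: it is mainly steroid use started after baseline, against two explicit bans.

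The size is 6.7 points of response rate per affected responder. The 0.013 and 0.056 tail probabilities, and the ranges in Step 5, rest on assumed numbers of users and assumed steroid response rates. A reader might infer that one steroid user would overturn the trial's conclusion. The documents do not support this, because the planned efficacy analysis is descriptive, no decision cut-off at 4 or 5 of 15 is stated, and alpha has no stated sidedness. Nor do they show that low-dose steroid use was intended or expected; the permission is only implied by the threshold.

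**What to change.** 1. The sponsor and investigator must reconcile the two items in 5.5.1 with each other, with 4.3.1, and with exclusions 3d and 5c. Which clinical rule applies is for them to decide; no dose is proposed here. The reconciled list should also make clear whether topical steroids used away from the scalp are meant.

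2. Add to 7.4.3: a subject who takes, after baseline and before the week-24 SALT, a medication that the reconciled list prohibits because it affects hair growth counts as a non-responder in the primary analysis. The start date matters, because inclusion 7 admits patients previously treated without response, and their earlier treatment should not trigger the rule.

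3. Provide a listing of such subjects and a sensitivity summary of the response rate that uses their observed SALT. Readers can then see how much depends on the rule.

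The cost is wording and one analysis rule. Concomitant medication is already collected, and N and the power calculation are unchanged. The one downside is that the primary response rate may be slightly lower.
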